Other Secondary Objective(s) 
To assess the efficacy of secukinumab 300 mg when administered in 2 mL AI in subjects with plaque-type psoriasis with respect to PASI score, IGA mod 2011 score, PASI 50 / 75 / 90 / 100 and IGA mod 2011 0 or 1 response up to Week 12 compared to placebo, and over time up to Week 52.To investigate the clinical safety and tolerability of secukinumab 300 mg 2 mL AI as assessed by vital signs, clinical laboratory variables, and adverse events monitoring, compared to placebo.To assess the subject usability (ability to follow instructions for use and potential use-related hazards) and satisfaction with the new secukinumab 2 mL AI utilizing a self-administered SIAQ and investigator/site staff observation of secukinumab 300 mg 2 mL AI administration.To investigate the effects of secukinumab 300 mg when administered in 2 mL AI with respect to DLQI 0 or 1 achievement and DLQI changes at Week 12 compared to placebo, and over time up to Week 52.	Endpoint(s) for other secondary objective(s) 
PASI score and IGA mod 2011 score at each visit up to week 52PASI 50, PASI 75, PASI 90, PASI 100 and IGA mod 2011 0 or 1 response at each visit up to week 52Treatment emergent adverse events, change from baseline to each study visit in clinical laboratory variables and vital signsSuccessful self-injection, subject use errors, item and domain scores from the SIAQ, change in SIAQ domain scoresDLQI 0 or 1 score at each visitChange from baseline in each of the seven DLQI scores and in the DLQI total score

Objective(s)	Endpoint(s)

3 Study design

This is a multicenter, randomized, double-blind, placebo-controlled, parallel-group trial in approximately 120 subjects with moderate to severe plaque-type psoriasis.

It is expected that subjects will be enrolled at around 30 study sites worldwide.

The study consists of 3 periods:

- Screening Period (of at least 1 week and up to 4 weeks between Screening and Randomization)

The screening period is used to assess eligibility of the subjects and to taper subjects off prohibited medications.

- Treatment Period 1 (of 12 weeks, double-blind between Randomization and Week 12 pre-dose)

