5.1 Inclusion criteria

Subjects eligible for inclusion in this study must meet all of the following criteria:

1. Subjects must be able to understand and communicate with the investigator and comply with the requirements of the study and must give a written, signed and dated informed consent before any study related activity is performed. Where relevant, a legal representative will also sign the informed study consent according to local laws and regulations.
2. Men or women of at least 18 years of age at the time of Screening.
3. Chronic plaque-type psoriasis present for at least 6 months and diagnosed before Randomization.
4. Moderate to severe psoriasis as defined at Randomization by:
 - PASI score of 12 or greater, and
 - IGA mod 2011 score of 3 or greater (based on a scale of 0 – 4), and
 - Body Surface Area (BSA) affected by plaque-type psoriasis of 10% or greater.
5. Candidate for systemic therapy.

This is defined as a subject having moderate to severe chronic plaque-type psoriasis that is inadequately controlled by

- Topical treatment and/or
- Phototherapy and/or
- Previous systemic therapy

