8.3.1 Investigator's Global Assessment (IGA mod 2011)

It is recommended that the same evaluator conduct the assessment throughout the study whenever possible.

The IGA mod 2011 used in this study is static, i.e., it refers exclusively to the subject's disease state at the time of the assessments, and does not attempt a comparison with any of the subject's previous disease states, whether at Randomization or at a previous visit.

The IGA mod 2011 score will be recorded in the eCRF.

Table 8-2 The IGA mod 2011 rating scale

Score	Short Description	Detailed Description
0	Clear	No signs of psoriasis. Post-inflammatory hyperpigmentation may be present.
1	Almost clear	Normal to pink coloration of lesions; no thickening; no to minimal focal scaling.
2	Mild	Pink to light red coloration; just detectable to mild thickening; predominantly fine scaling.
3	Moderate	Dull bright red, clearly distinguishable erythema; clearly distinguishable to moderate thickening; moderate scaling.
4	Severe	Bright to deep dark red coloration; severe thickening with hard edges; severe/coarse scaling covering almost all or all lesions.

Note: Involvement of nails is not part of the assessment

Based on this scale, the following criteria apply:

- A subject will be eligible to participate in the study if she/he has an IGA mod 2011 score at the Randomization Visit of 3 or 4.
- A subject will be considered as IGA mod 2011 0 or 1 responder if she/he achieves a score of 0 or 1, and improved by at least 2 points on the IGA scale at a given time point compared to baseline.

8.3.2 Assessment of total Body Surface Area (BSA) and Psoriasis Area Severity Index (PASI)

The investigator or qualified designee will complete the PASI assessment. Whenever possible, PASI assessments should be performed by the same evaluator throughout the study.

The total BSA affected by plaque-type psoriasis will be estimated as first step of PASI calculation from the percentages of areas affected, including head, trunk, upper limbs and lower limbs (see [Table 8-3](#)). The following calculations will be done: each reported percentage will be multiplied by its respective body region corresponding factor (head = 0.1, trunk = 0.3, upper limbs = 0.2, lower limbs = 0.4). The resulting 4 percentages will be added up to estimate the total BSA affected by plaque-type psoriasis.

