12.6.3 Health-related Quality of Life - Dermatology Life Quality Index (DLQI)

Summaries will be based on the FAS and will be presented separately for each treatment group.

For each of the seven scores the percentage change from baseline will be derived. Summary statistics will be provided for absolute values as well as for the percentage change by visit and treatment group.

The absolute value and the percentage change from baseline of DLQI total score will be analyzed with the Van-Elteren test using type-II weights, for between-treatment comparison of the two secukinumab treatment groups versus placebo. The Van-Elteren test will be performed at each visit. Language of the questionnaire will be the stratum adjusted for in the Van-Elteren test. In addition, stratified Hodges-Lehmann estimates for the median as well as confidence intervals will be derived for the absolute values and percentage change to baseline for each treatment group as well as for treatment comparison between two secukinumab treatment groups versus placebo.

It is understood that conclusions obtained from the confidence intervals of these estimates (mean or Hodges-Lehmann estimates for the median) will not be completely consistent with the testing results (Van-Elteren test) which constitute the key analysis for drawing conclusions.

In addition, summary statistics will be provided for number of subjects achieving DLQI 0 or 1. Treatment groups will be compared by means of Fisher's exact test.

[figure not shown]

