- **PASI 100 response / remission:** complete clearing of psoriasis (PASI=0)

2.5.1.2 Definition of IGA mod 2011 score and IGA mod 2011 0 or 1 response

The IGA mod 2011 rating scale for overall psoriatic disease (shown in [Table 2-6](#)) has been developed based on a previous version of the scale used in secukinumab phase II studies, and has been updated in collaboration with health authorities (in particular the FDA). The explanations/descriptions of the points on the scale have been improved to ensure appropriate differentiation between the points. It is recommended that the same evaluator conducts the assessments throughout the study whenever possible.

The IGA mod 2011 used in this study is static, i.e., it refers exclusively to the subject's disease state at the time of the assessments, and does not attempt a comparison with any of the subject's previous disease states, whether at baseline or at a previous visit.

Table 2-6 The IGA mod 2011 rating scale

Score	Short Description	Detailed Description
0	Clear	No signs of psoriasis. Post-inflammatory hyperpigmentation may be present.
1	Almost clear	Normal to pink coloration of lesions; no thickening; no to minimal focal scaling.
2	Mild	Pink to light red coloration; just detectable to mild thickening; predominantly fine scaling.
3	Moderate	Dull bright red, clearly distinguishable erythema; clearly distinguishable to moderate thickening; moderate scaling.
4	Severe	Bright to deep dark red coloration; severe thickening with hard edges; severe / coarse scaling covering almost all or all lesions.

Note: Involvement of nails is not part of the assessment.

Subjects require an IGA mod 2011 score at randomization of 3 or 4 in order to participate in the study. Based on this scale, subjects will be considered as **IGA mod 2011 0 or 1 responder** if they achieve a score of 0 or 1 and improve by at least 2 points on the IGA mod 2011 scale compared to baseline.

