2.12 Patient-reported outcomes

Summaries will be based on the FAS and will be presented separately for each treatment group.

For DLQI, missing values will be replaced by LOCF. Baseline values will not be carried forward. If no pre-treatment value exists, values obtained after first dose of treatment can be used as baseline only if it was collected on the same day as first dose. In addition, missing baseline (PROs) values will be replaced by the means or modes of non-missing baseline values stratified by age group (<65 years, 65 years and older) and sex, for continuous scale or categorical/ordinal scale, respectively.

Dermatology Life Quality Index

The DLQI measures functional disability of subjects with dermatological disorders that are greater than 18 years of age and had been utilized as a relevant clinical measure in atopic dermatitis, as well as other dermatitis clinical trials. The DLQI is a simple, validated, self-administered 10-item questionnaire. The instrument contains six functional scales (i.e., symptoms and feeling, daily activities, leisure, work and school, personal relationships, treatment). For the DLQI, each question will be answered with the following response: “not at all”, “a little”, “a lot”, or “very much”. “Not relevant” is also a valid response. Seven scores will be derived from the DLQI: the total score of each of the six dimensions as well as the total score over all items. The higher the score, the more quality of life is impaired.

For each of the seven scores, the percentage change from baseline will be derived. Summary statistics will be provided for absolute values as well as for the percentage change by visit and treatment group.

In addition, summary statistics will be provided for number of subjects achieving DLQI 0 or 1. Treatment groups will be compared by Fisher’s exact test.

Self-Injection Assessment Questionnaire (SIAQ)

All SIAQ analyses will be based on the Safety Set.

Summary statistics for the absolute values of the domain scores at Randomization (baseline) will be provided by treatment group including total for the PRE-module and the POST-module. The number and percentage of subjects in each of the 5 categories (likert scale) for each item will be presented by visit and treatment group including total.

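### DLQI 0/1 achievement carries no baseline condition, so subjects who enter at 0 or 1 and stay there count as achievers and may dilute the difference from placebo

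*Protocol*

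**What the plan says.** Protocol Table 2-1 states the objective as an effect "with respect to DLQI 0 or 1 achievement and DLQI changes at Week 12 compared to placebo". The matching endpoint in the same table is simply a DLQI score of 0 or 1 at each visit. It is an other secondary endpoint, outside the H1–H3 testing sequence (Protocol 12.5, SAP 2.6.2).

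For the analysis, SAP 2.12 says that "summary statistics will be provided for number of subjects achieving DLQI 0 or 1", and Protocol 12.6.3 has the same wording. On the population, SAP 2.12 says "Summaries will be based on the FAS and will be presented separately for each treatment group". On the comparison, Protocol 12.6.3 says "Treatment groups will be compared by means of" Fisher's exact test, and SAP 2.12 agrees. Neither document requires a baseline DLQI above 1 or an improvement, or uses baseline DLQI in this comparison.

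Protocol 5.1 defines disease severity at entry by skin measures only: "PASI score of 12 or greater, and" IGA mod 2011 of at least 3 and body surface area of at least 10%. There is no DLQI threshold.

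Missing DLQI values are filled by last observation carried forward, but SAP 2.12 adds: "Baseline values will not be carried forward". The same section lets a value taken after the first dose on the same day serve as baseline. It replaces missing baselines by means or modes within age group and sex.

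SAP section 4 removes the Van Elteren test and the Hodges-Lehmann estimates for DLQI total. Fisher's test on DLQI 0/1 is then the only between-arm DLQI test left in the SAP.

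**The concern.** The objective speaks of achievement, but the endpoint records a state. A subject already at 0 or 1 at entry has nothing to achieve, yet counts as a success in whichever arm they are in, provided the later score is still 0 or 1. Such subjects say little about the treatment effect and sit in both numerator and denominator.

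At stake is the reading of this one endpoint. The achievement rates would mix the effect of treatment with status at entry, the placebo rate would rise most, and the contrast with placebo would be blunted. This matters somewhat more than the endpoint's rank suggests, because no other between-arm DLQI test remains in the SAP.

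**Working it through.** **The plan's own figure.** The documents give no power or expected rate for DLQI 0/1. The stated power for the co-primary endpoints (Protocol 12.8.1) checks the method: 40 per group, placebo 8%, active 62% (PASI 75) or 55% (IGA 0/1), Fisher's exact test, one-sided 2.5%. Exact enumeration gives 99.97% and 99.72%, which agrees with the stated value of above 99%.

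**Inputs for DLQI.** From the documents: 40 on the auto-injector and 40 on pooled placebo (2:2:1:1 of 120, placebo groups combined to Week 12), and Fisher's exact test. Power is taken at one-sided 2.5%; with equal arms, two-sided 5% gives the same result. Assumed, because the documents are silent:
- f, the share entering at DLQI 0/1;
- p1 and p0, the true Week 12 rates on auto-injector and placebo among the rest;
- m1 and m0, the probabilities that a subject who enters at 0/1 is still there at Week 12.

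**Formula.** Observed rate = f·m + (1-f)·p in each arm, so

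observed difference = (1-f)(p1-p0) + f(m1-m0).

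If m1 = m0, the difference shrinks by the factor (1-f). If both equal 1, the placebo rate rises by f(1-p0) and the active rate by f(1-p1). Placebo rises more because p0 is lower.

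**Example, f = 5%, p1 = 60%, p0 = 8%, m1 = m0 = 1.**
- Placebo: 0.05 + 0.95 × 0.08 = 12.6%.
- Auto-injector: 0.05 + 0.95 × 0.60 = 62.0%.
- Difference: 49.4 points against 52 (0.95 × 52 = 49.4).
- At f = 10%: 64.0% against 17.2%, difference 46.8.

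**Power with m1 = m0 = 1.** As written uses 40 per arm. Restricted to baseline of 2 or more leaves 38 per arm at f = 5% and 36 at f = 10%.

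| True rates | f | As written | Restricted |
|---|---|---|---|
| 60% vs 8% | 5% | 99.7% | 99.9% |
| 60% vs 8% | 10% | 99.0% | 99.8% |
| 50% vs 8% | 5% | 96.5% | 98.6% |
| 50% vs 8% | 10% | 92.7% | 97.9% |
| 30% vs 8% | 5% | 52.6% | 62.0% |
| 30% vs 8% | 10% | 42.8% | 58.5% |

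The restricted analysis has more power in every row despite fewer subjects. The gain is trivial for a large effect and visible only for a small one.

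**When dilution does not occur.** The difference shrinks only if m1-m0 is below p1-p0. With 60% vs 8%, f = 5%, m1 = 1 and m0 = 0.5, it is 0.95 × 52 + 5 × 0.5 = 51.9 points, almost unchanged from 52.

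**An alternative that does not work.** Keeping these subjects in the denominator as non-achievers gives 57.0% against 7.6%. The placebo rate falls, but the difference is still 49.4 points. Only restriction restores 52.

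**The case against.** The strongest reply is that the endpoint is a state, defined consistently. A score of 0–1 is described in SAP 5.7.1 as no effect on the subject's life, and the proportion of all subjects in that state is a legitimate quantity. Change from baseline in the DLQI scores is a companion endpoint. That stands in part: only the word achievement creates friction with the definition, and the companion endpoint is purely descriptive in the SAP.

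Second, f is unknown and may be small in a population selected for moderate to severe, inadequately controlled disease. That stands. With a large true effect the loss of power is negligible.

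Third, a reader might infer that everyone entering at 0/1 is automatically an achiever. The documents do not support this: the baseline score is not carried forward, so a post-baseline score of 0 or 1 is needed.

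Fourth, a reader might infer that the sponsor guarded IGA against this problem and overlooked DLQI. The IGA rule does require that a subject "achieves a score of 0 or 1, and improved by at least 2 points on the IGA scale" (Protocol 8.3.1; SAP 2.5.1.2 likewise). But entry already requires IGA of 3 or 4, so any eligible subject who reaches 0 or 1 has improved by at least 2 points. For IGA the entry criterion does the work. The useful contrast is that DLQI has no such floor.

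Fifth, the restriction needs care, because the SAP allows imputed and same-day post-dose baselines. That stands and is covered in the fix.

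**Conclusion.** The gap in the definition is real: no baseline condition and no DLQI floor at entry. Its consequence is conditional. If subjects entering at 0/1 remain there about equally in both arms, the difference from placebo is diluted by the factor (1-f). At f = 5% and 60% vs 8% that is 2.6 points, about one subject in 40. The power cost at f = 5% runs from 0.2 percentage points at that effect to 9.4 at 30% vs 8%. All these rates, and f itself, are assumptions; the documents give no DLQI distribution.

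It would be wrong to read this as bias in favour of secukinumab. Such subjects are balanced by randomisation in expectation, and equal persistence pulls the result towards no difference. Nor is dilution certain, since placebo subjects may lose 0/1 status more often. The co-primary and key secondary tests and the sample size are untouched. This is a refinement to consider, not a required correction.

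**What to change.** In SAP 2.12, with matching wording in Protocol 12.6.3:

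- Report by arm the number of subjects with baseline DLQI total of 0 or 1.
- Analyse Week 12 DLQI 0/1 among full-analysis-set subjects with an observed, pre-dose baseline total of 2 or more, and show that denominator. Do not use imputed or post-dose baselines to decide who is in it.
- Keep the count in the whole full analysis set as supportive.
- Compare auto-injector with placebo by the logistic model already used for the other binary endpoints, with weight stratum and baseline DLQI total as covariates. Fall back to Fisher's exact test if the model does not converge; SAP 5.4.3 itself warns that this can happen when response rates are low.

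The cost is SAP wording, one denominator flag and one model; no new data are needed. A few subjects leave this one analysis, including any without an observed pre-dose baseline. Because selection rests on a value observed before the first dose, the comparison remains a randomised one.

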4.1 Rationale for study design

The intent of this study is to assess a 2 mL auto-injector form for the administration of 300 mg of secukinumab instead of two injections of 1 mL pre-filled syringes of 150 mg each, to psoriasis subjects that are treated with secukinumab at the recommended dose.

This 52-week, double-blind, randomized, parallel-group, and placebo-controlled study is using the recommended dose of 300 mg secukinumab which has been approved for the treatment of moderate to severe psoriasis in adults.

The study has been designed in accordance with Health Authorities guidelines and feedback on the clinical development program for the 2 mL auto-injector, including the United States Food and Drug Administration (FDA). The principle of a 2 mL s.c. injection is supported by a patient education document published by the National Institute of Health (NIH) that outlines the possibility to administer more than 1 mL of volume (NIH 2016). Based upon a recently conducted Novartis relative bioavailability study (CAIN457A2107) that assessed the 300 mg dose with a 2 mL s.c. injection using different devices, the pharmacokinetic data with 2 mL s.c. were similar to two marketed forms of 1 mL s.c. (pre-filled syringe and auto-injector/pen) and safety data showed no issues with 2 mL s.c. injections, including local tolerability. Therefore, it is appropriate to initiate study CAIN457A2325.

The primary endpoint of this study is at Week 12. This will allow for assessment of efficacy at a point in time for which efficacy data of current approved biologic therapies are available and which was the primary endpoint for the phase III studies with secukinumab in psoriasis, including those studies that introduced the liquid formulations (1 mL pre-filled syringe in CAIN457A2308, and 1 mL auto-injector in CAIN457A2309; Blauvelt et al 2014, Paul C et al 2015).

Overall, this study will assess the efficacy, [redacted] safety ([redacted]) and tolerability of secukinumab when used both, short-term (up to 12 weeks) and long-term (up to 52 weeks) and includes an usability and satisfaction assessment (ability to follow instruction for use and potential use-related hazards) and satisfaction) of secukinumab with a 2 mL auto-injector. These data will support the registration of secukinumab 300 mg 2 mL auto-injector.

The subject population will be described in more detail in [Section 5](#) below.

4.2 Rationale for dose/regimen and duration of treatment

The placebo-controlled study design was chosen to demonstrate the efficacy of 300 mg secukinumab administered with a 2 mL auto-injector in adult subjects suffering from moderate to severe psoriasis compared to placebo. The selected dose regimen for this study with an initial weekly schedule up to 4 weeks followed by a s.c administration of every four weeks up to Week 48 is in line with the posology and method of administration as described in the approved product labelling. The selected design with the two injections of secukinumab 1 mL pre-filled syringes will also allow the comparison of the [redacted] and safety profile with the secukinumab 300 mg 2 mL auto-injector.

4.3 Rationale for choice of comparator

Due to the nature of psoriasis and the outcome measures for the primary and the key secondary endpoints used (PASI 75, 90 and IGA mod 2011 0 or 1), a placebo arm is necessary for reliable results on efficacy and safety. Moreover, the inclusion of a placebo group is in accordance with health authority guidelines ([CHMP Psoriasis Guideline 2004](#)). The duration of 3 months treatment within the placebo group up to the primary endpoint at Week 12 is accepted for

the indication of plaque-type psoriasis. Subjects from the placebo group that will not achieve PASI 90 after Week 12 will receive secukinumab.

An arm with secukinumab 300 mg as 2 injections of 1 mL PFS has been added to assess [REDACTED] and as a reference for comparisons of efficacy and safety with secukinumab 300 mg 2 mL AI.

4.4 Purpose and timing of interim analyses/design adaptations

An analysis is planned to be performed after all subjects have completed the Week 16 visit to assess the [REDACTED] data up to Week 16 with the coprimary endpoints.

All data up to Week 16 will be collected with the clinical team being blinded. The designated Novartis personnel (eg, statistician, programmer and a clinical representative) will be unblinded following database lock for the Week 16 analysis after all subjects have completed Week 16. Investigators, site personnel, and subjects will remain blinded until the end of the study.

It is planned that data from the Week 16 analysis will be used for submission to the Health Authorities. Trial modifications are not planned based on any Week 16 analysis.

Additional analyses are not planned, they may be performed to support Health Authorities interactions, as necessary.

